8.1 Sample size determination

This study is a randomized, three group (5, 10, 20 ml bupivacaine), mixed study using the primary endpoint of ambulation or gait velocity over 10 meters (10 meter walk test) on POD 1. The data from this preliminary study will be used to generate hypotheses for future trials. We performed an effect size calculation based on the ratio of the hypothesized differences and the standard deviation based on our current experience. Based on physical therapy team experience, patients are currently able to ambulate 10 meters in approximately 45 seconds on postoperative day one with 20 ml of local anesthetic injected into the adductor canal. The physical therapy team feels that ambulation velocity is generally limited by weakness and pain. However, previous retrospective research done at our own institution demonstrated that adductor canal block patients were able to ambulate more effectively than those patients receiving a femoral nerve catheter (i.e. those with a more profound motor blockade). We therefore hypothesize that decreasing the dose of local anesthetic delivered into the adductor canal will decrease the amount of time required to ambulate 10 m and that this difference could approach 15 seconds. We hypothesize that the standard deviation may be of similar magnitude. With a power of 0.8 and significance level of 0.05, 16 patients are required per group. Increasing enrollment to 20 patients per group will allow for patient drop out.

9. Risks and benefits of trial participation

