7.2 Subject withdrawals

At any point prior to or during the intervention period, the subject's clinical care team or a study physician may decide the subject should be withdrawn from the study. If a subject is withdrawn from the study for any reason the subject will then be followed according to the standard of care follow-up plan.

Study intervention will immediately stop and subject's clinical care team and a study physician will be immediately notified if one of the following occurs:

- 1) The subject suffers a severe adverse perioperative outcome that precludes participation in physical therapy or measurements of motor strength or sensory examination

In the event the study method is terminated, the reason for termination will be documented on a case report form.

8. Data analysis and statistical considerations

All data will be summarized using standard descriptive statistics, including mean, standard deviation, minimum, maximum, median, inter-quartile range, and confidence intervals, as appropriate. The data will be presented graphically (where possible) using scatter plots, profile plots, or histograms. Data analyses will be performed on an intent-to-treat basis using SAS (SAS Institute Inc., Cary, NC; version 8.2 or greater) or Minitab (Quality Plaza, State College, PA; version 13.0 or greater). The primary analyses will consist of comparing the three study volumes of injection for superiority. For all tests, statistical significance will be defined as a p-value less than 0.05. ANOVA and two-sample t-test will be used to compare the data between the three groups or between any two individual groups. Repeated measures ANOVA will be used to analyze multiple follow-up data points. Patients with missing longitudinal data will be handled by either using data imputation methods to replace the missing data or via the use of repeated measures ANOVA to better approximate the average values at each time point. Bonferroni correction will be utilized to counteract the problem of [multiple comparisons](#) and control the [familywise error rate](#).

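### The 80% power claimed for 16 patients per group uses an unadjusted 0.05 level; under the plan's own Bonferroni-corrected pairwise tests it is about 62%

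*Combined protocol and SAP*

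**What the plan says.** Section 8.1 sizes the trial on the POD 1 10-meter walk test. On the effect of lowering the volume it says "this difference could approach 15 seconds. We hypothesize that the standard deviation may be of similar magnitude". It then concludes: "With a power of 0.8 and significance level of 0.05, 16 patients are required per group". Enrolment is set above that figure: "Increasing enrollment to 20 patients per group will allow for patient drop out". No dropout rate, test, sidedness, pattern for the three group means or multiplicity adjustment is given. The same section describes the purpose: "The data from this preliminary study will be used to generate hypotheses for future trials".

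Section 8 describes the analysis: "ANOVA and two-sample t-test will be used to compare the data between the three groups or between any two individual groups". On the threshold it says "For all tests, statistical significance will be defined as a p-value less than 0.05". It closes with "Bonferroni correction will be utilized to counteract the problem of" multiple comparisons, with control of the familywise error rate as the stated aim. It does not say which comparisons, or how many, form the Bonferroni family, or whether the 0.05 threshold applies to raw or adjusted p-values.

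**The concern.** The sample size and the pairwise analysis use different error rates. Section 8.1 spends the full 0.05 on one comparison, whereas section 8 promises to divide it among several. The stated power of 0.8 therefore does not belong to the corrected pairwise tests that would show which volumes differ.

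Two things are at stake. First, a non-significant pairwise result could be read as coming from an 80% powered comparison, and so as evidence that volumes perform alike, when the real chance of missing the planning difference is much higher. Second, with the family and threshold unnamed, the significance rule is open once data are seen: a raw p-value of 0.03 is significant on one reading and not on another.

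**Working it through.** **Inputs.** From section 8.1: difference 15 s, SD 15 s (reading similar magnitude as equal, so standardised difference d = 15/15 = 1), power 0.8, significance level 0.05, 16 per group raised to 20. From section 5: 1:1:1 allocation. Assumed because not stated: two-sided tests, and a Bonferroni family of three pairs (5 v 10, 5 v 20 and 10 v 20 ml), so the level per test is 0.05/3 = 0.0167. A family of two (each lower volume against 20 ml, level 0.05/2 = 0.025) is also shown.

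**Step 1: reproduce the plan's figure.** Two-group normal formula, unadjusted:

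n per group = 2(z₀.₉₇₅ + z₀.₈₀)²/d² = 2(1.960 + 0.842)²/1² = 15.7, rounded up to 16.

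The exact t calculation gives 17. A one-sided 0.05 gives 13. An omnibus ANOVA F-test at 0.05 also gives 16 if 10 ml has the same mean as either 5 ml or 20 ml, but 21 if it lies midway. So 16 is reproducible, but the text does not show which calculation produced it.

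**Step 2: power under the planned pairwise analysis.** For a two-sample t-test with n per group, the noncentrality is d√(n/2) with 2n − 2 degrees of freedom. That is 2.83 on 30 df at n = 16, and 3.16 on 38 df at n = 20. At level 0.0167 the two-sided critical values are 2.54 and 2.50.

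| Level per test | n = 16, exact t | n = 16, normal | n = 20, exact t | n = 20, normal |
|---|---|---|---|---|
| 0.05 (no correction) | 0.781 | 0.807 | 0.869 | 0.885 |
| 0.025 (two comparisons) | 0.680 | 0.721 | 0.793 | 0.821 |
| 0.0167 (three pairs) | 0.617 | 0.668 | 0.742 | 0.779 |

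Using the error variance pooled over all three groups (3n − 3 df) changes little: 0.635 and 0.754 for three pairs, 0.694 and 0.803 for two comparisons.

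**Step 3: detectable difference.** At level 0.0167, 80% power needs d = 1.202 at n = 16 (× 15 s = 18.0 s) and d = 1.064 at n = 20 (× 15 s = 16.0 s).

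**Step 4: the omnibus reading.** The noncentral F at 0.05 has power 0.814 (n = 16) and 0.900 (n = 20) if 10 ml equals an end group, for example means of 30, 30 and 45 s. If 10 ml is midway (30, 37.5 and 45 s), power is 0.686 and 0.793.

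**The case against.** The strongest reply is that 16 is not a miscalculation. It follows from the stated inputs by two routes, and on the omnibus ANOVA route no pairwise correction is needed. ANOVA is the first test that section 8 names. That stands as a statement about the arithmetic. But section 8 does not make the omnibus test primary, the 80% then holds only if 10 ml matches an end group, and an omnibus result does not say which volumes differ.

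A second reply concerns the definition of power. The chance that at least one of the three Bonferroni tests is significant is about 0.78 at n = 16 and 0.87 at n = 20 (simulation) when 10 ml equals an end group, close to what was promised. With 10 ml midway it falls to 0.65 and 0.77. Section 8.1 supports neither pattern, so this helps only in the favourable case.

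Third, the three-pair family is assumed, and the hypothesis about lowering the dose from 20 ml fits two comparisons equally well. That is fair. With two comparisons and all 20 per group evaluable, the normal (0.82) and pooled-error (0.80) calculations reach 80%. With 16 evaluable, the number the plan sizes for, no corrected version does: the range is 0.62 to 0.72.

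Fourth, the inputs are loose. Three-pair power at n = 16 is 0.83 if the SD is 12 s and 0.44 if it is 18 s, a wider spread than the Bonferroni effect. This argues for presenting the restated power as conditional on 15 s and SD 15 s, not for leaving the 80% in place. Part of the shortfall is also not multiplicity: exact t power without correction is already 0.78.

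**Conclusion.** The concern holds. The figure of 16 is reproducible at an unadjusted two-sided 0.05, but the plan's corrected pairwise tests do not have 80% power at that number for the difference used to size the trial. Under the three-pair correction, power is about 62% at 16 evaluable per group and 74% at 20. The chance of missing a true 15 s difference at 16 is therefore 1 − 0.62 = 38%, rather than 20%. With two comparisons the power is 68% and 79% (exact t).

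These figures rest on a 15 s difference, SD 15 s, equal groups, two-sided tests and an assumed family. The conclusion that 16 evaluable per group falls short of 80% does not depend on choosing two or three comparisons, nor on exact t, normal or pooled-error calculation. Because the trial is preliminary and its inputs are rough, the consequence is a misstated power and an open significance rule, not a reason to enlarge the study.

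**What to change.** **Section 8.** State that the Bonferroni family is the three pairwise comparisons of the POD 1 10-meter walk test, and that 0.05 applies to Bonferroni-adjusted p-values (equivalently, raw p against 0.0167).

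**Section 8.1.** Name the test and replace the power sentence with: For a 15 s difference (SD 15 s) between two volumes, two-sided two-sample t-test at 0.0167, power is about 62% with 16 evaluable per group and 74% with 20; the difference detectable with 80% power is 18 s and 16 s respectively. If the investigators intend only the two comparisons with 20 ml, they should say so and give 68% and 79% at 0.025.

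**Optional alternative, in place of Bonferroni.** For the primary endpoint, run the omnibus F-test at 0.05 and, only if it is significant, unadjusted pairwise tests with pooled error. With exactly three groups this controls the familywise error rate (simulated at 0.050). Section 8.1 should then give its power for 5 ml versus 20 ml instead: 0.742 (10 ml equal to 5 ml) or 0.675 (midway) at n = 16, and 0.845 or 0.786 at n = 20. This too is below 80% at 16 evaluable.

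**Cost.** Wording in two sections and a less favourable stated power. No added patients and no change to conduct.

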9.1 Potential risks

It is possible that larger volumes of local anesthetic could track proximally within the adductor canal and result in significant motor weakness to the quadriceps muscle. Significant weakness may be a risk factor for falls. It is also possible that decreased volumes may result in increased pain and difficulty participating with physical therapy. Inherent risks associated with nerve blockade include bleeding, infection, nerve damage, allergic reaction to local anesthetic, etc. However, standard of care is currently for patients presenting for TKA to receive an adductor canal block and therefore these would not represent additional risks.

Risks associated with loss of confidentiality

There is a risk that information recorded about subjects will be shared with people who would not normally have access to this information.

Unknown risks

This study may involve risks to the subject which are currently unforeseeable. We will inform subjects as soon as possible if we discover any information that may affect the subject's health, welfare, or decision to be in this study.

9.2 Mitigation of potential risks

The risk of increased quadriceps weakness and fall will be minimized by the involvement of physical therapists for all postoperative motor strength evaluations. The risk of inadequate analgesia will be minimized by the availability of supplemental oral and potentially intravenous analgesics.

9.3 Potential benefits and risk-to-benefit ratio

While there are risks to involvement in this research trial, they generally should be infrequent and not difficult to manage. The potential benefits of this research could result in quicker hospital discharge time with resulting decreases in costs. Patients may also benefit from a decreased risk of infection if they are able to leave the hospital sooner or improved implant function if early postoperative rehabilitation is optimized.

10. Adverse events and unanticipated problems

10.1 Adverse event definitions

Adverse event (AE)

An adverse event is defined as any untoward or unfavorable medical occurrence in a human subject including any abnormal sign, symptom, or disease temporally associated with the SSACNB or study procedure that appears or worsens during the study or study follow-up period. AEs may be anticipated (e.g., redness/soreness at injection site) or unanticipated (e.g., bleeding/infection/nerve damage). Adverse event information will be collected throughout the study from informed consent through resolution of the AE and documented on the case report form or the standard follow-up questionnaire.

All AEs (anticipated and unanticipated) will be recorded on one of the study data sheets (case report form or standard questionnaire) by a study investigator or study staff. In the event of an unanticipated AE, the primary anesthesia team caring for the subject will intervene as deemed appropriate. These are the same provisions that would be made for any non-study case and represents standard practice.

Serious adverse event (SAE)

A serious adverse event is defined as any adverse event that meets one of the following criteria:

- Results in death; OR
- Is life-threatening; OR
- Requires hospitalization or prolongs existing hospitalization; OR
- Results in significant or persistent disability or incapacity; OR
- Results in a congenital anomaly/birth defect

Given the minimal risk associated with the use of SSACB and the study procedures, no serious adverse events (SAEs) are anticipated. If a SAE occurs, the study primary and co-primary investigators will be immediately notified and further enrollment in the study will be halted until a full explanation of the cause of the event and its relationship to the SSACB and/or study procedure is understood. The IRB will be notified and re-initiation of study enrollment will not occur until approved by the IRB.

Unanticipated problem (UP)

An unanticipated problem is defined as an event that meets all of the following criteria:

- 1) Unexpected in severity, nature, or frequency given the research procedures and the characteristics of the subject population (i.e., problems that are not described in this protocol or other study documents); AND
- 2) Related or possible related to participation in the research; AND
- 3) Suggests that research places subjects or others at a greater risk of harm related to the research than was previously known or recognized.

10.2 Severity assessment

The severity of all adverse events will be assessed according to the following scale:

- Mild = not requiring treatment or intervention
- Moderate = resolved with treatment/intervention
- Severe = inability to carry on normal activities and required professional medical attention

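### The adverse event severity scale in section 10.2 mixes treatment, resolution and function, so some events fit no grade, some fit two, and disabling motor weakness can be Mild or Severe

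*Combined protocol and SAP*

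**What the plan says.** Section 10.2 sets one scale for every event: "The severity of all adverse events will be assessed according to the following scale". Its three grades are:

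- "Mild = not requiring treatment or intervention"
- "Moderate = resolved with treatment/intervention"
- "Severe = inability to carry on normal activities and required professional medical attention"

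Section 9.1 names a different possible harm at each end of the volume range. One possibility is that "larger volumes of local anesthetic could track proximally within the adductor canal and result in significant motor weakness to the quadriceps muscle". The other is that "decreased volumes may result in increased pain and difficulty participating with physical therapy". For pain, section 9.2 states: "The risk of inadequate analgesia will be minimized by the availability of supplemental oral and potentially intravenous analgesics". For weakness and falls it relies on physical therapists being involved in the postoperative strength evaluations and names no treatment.

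The adverse event definition in section 10.1 is wide enough to take in weakness and pain, but it mentions neither. Both are followed separately as secondary outcomes in section 2.2. Section 8 says that all data will be summarized descriptively and contains nothing specific to adverse event severity.

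**The concern.** A severity scale should give each event exactly one grade, and a higher grade should mean a worse event. This one changes its criterion at each step. Mild depends on need for treatment, Moderate on treatment and its success, and Severe on lost function together with medical attention. Two assessors can follow the text faithfully and grade the same event differently, or find no grade for it.

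The weakness matters more here than in many trials because the volumes may trade one kind of harm for another. If the scale handles weakness and pain by different rules, a table of severities can reflect the mix of event types rather than how badly patients were affected. Severity also enters the definition of an unanticipated problem in section 10.1, and the blinded safety reviews in sections 11.1 and 12.3 look at study data, so unstable grades would make that material harder to read.

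**Working it through.** The plan gives no adverse event rates or severity figures, so there is no stated figure to reproduce. The sample size of 16 per group in section 8.1 concerns the walk test and plays no part here.

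**Step 1: apply the three definitions to event patterns.**

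| Event pattern | Mild? | Moderate? | Severe? | Result |
|---|---|---|---|---|
| Treated, not resolved, patient functions normally | No, treatment was needed | No, not resolved | No, function is kept | No grade |
| Disabling, received medical attention, resolved with treatment | No, treatment was needed | Yes | Yes | Two grades |
| Weakness prevents walking, wears off untreated; routine inpatient care **not** counted as medical attention | Yes | No, no treatment | No, second condition fails | Mild |
| Same weakness; routine inpatient care **counted** as medical attention | Wording still met unless that care is an intervention | No | Yes | Severe |

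The last two rows describe the same patient. The grade moves from lowest to highest on a term that section 10.2 does not define for inpatients.

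**Step 2: see what this could do to a descriptive summary.** All rates here are assumed. Take 20 patients per arm (section 8.1). In the 20 ml arm let 30% have a weakness event and 10% a pain event; in the 5 ml arm let 10% have weakness and 30% pain. Each arm then has 8 events: 6 weakness + 2 pain at 20 ml, and 2 weakness + 6 pain at 5 ml. Let *a* be the share of pain events, and *b* the share of weakness events, that are treated and resolve. With no event graded Severe:

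- Moderate events at 20 ml = 2*a* + 6*b*
- Moderate events at 5 ml = 6*a* + 2*b*

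| *a* | *b* | 20 ml | 5 ml |
|---|---|---|---|
| 1.0 | 0 | 2.0 of 8 = 25% | 6.0 of 8 = 75% |
| 0.9 | 0.2 | 1.8 + 1.2 = 3.0 of 8 = 37.5% | 5.4 + 0.4 = 5.8 of 8 = 72.5% |
| 0.7 | 0.5 | 1.4 + 3.0 = 4.4 of 8 = 55% | 4.2 + 1.0 = 5.2 of 8 = 65% |
| 0.5 | 0.5 | 1.0 + 3.0 = 4.0 of 8 = 50% | 3.0 + 1.0 = 4.0 of 8 = 50% |

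The gap has the factor (*a* − *b*): (6*a* + 2*b*) − (2*a* + 6*b*) = 4(*a* − *b*). It disappears when the two kinds of event are treated and resolve equally often.

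**Step 3: change only the reading of medical attention.** Keep *a* = 1 and *b* = 0, suppose that every weakness event prevents walking, and count routine inpatient care. The weakness events become Severe: 6 of 20 patients at 20 ml against 2 of 20 at 5 ml. The arm that looked milder in the first row of Step 2 now has more Severe events, although no patient's condition has changed.

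**The case against.** The strongest reply is that little depends on these grades. Quadriceps and adductor strength are measured at baseline, 15 minutes after the block, and 24 and 48 hours after surgery. Pain is rated at 24 and 48 hours, and opioid use is recorded. Under section 5.1 the physical therapy staff and the study member collecting pre- and postoperative data are blinded to volume. Section 8 plans no comparison of severity between arms. All of this stands, and it limits the consequence to descriptive safety summaries. It does not repair the scale: blinding does not help when the definitions themselves overlap or leave gaps.

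A reader might infer three stronger things, and the documents support none of them.

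- **That the scale necessarily ranks large-volume harm below small-volume harm.** Steps 2 and 3 show that the direction depends on how often each kind of event is treated and on what counts as medical attention. Treated pain is Moderate only if it resolves. The background analgesia in section 7 is standard care that study involvement does not alter, so treated pain is expected in every arm.
- **That falls would be under-reported.** Section 10.3 names falls separately and deems them probably related. The seriousness criteria in section 10.1 operate independently of this scale.
- **That misgrading would change who is withdrawn.** The stop criterion in section 7.2 uses the word severe, but it carries its own functional test and does not refer to section 10.2.

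**Conclusion.** The scale is defective as written. It covers all adverse events, yet one plausible pattern has no grade, another has two, and disabling weakness that wears off untreated can be Mild or Severe depending on an undefined term. These conclusions follow from the three definitions alone and need no assumption about rates.

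Any effect on the comparison of arms is only a possibility. It requires that weakness and postoperative pain be logged as adverse events, which the plan neither says nor excludes, and that the mix of these events differ by volume, which section 9.1 presents only as possible. The percentages above are illustrations on assumed rates. Neither direction nor size can be derived from the documents, and the walk test on postoperative day 1 is unaffected. The point is worth correcting because the correction is so cheap.

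**What to change.** Rewrite section 10.2 on one exhaustive, mutually exclusive axis, namely functional interference judged against the expected postoperative course:

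- Mild: does not interfere with planned physical therapy or daily care.
- Moderate: limits it.
- Severe: prevents it.

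The reference to the expected course is needed because patients this soon after knee replacement are not at their usual level of function.

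Record treatment given (yes/no) and outcome (resolved, ongoing, sequelae) as separate adverse event fields. The case report form is cited as Appendix B but is not among the documents reviewed, so check first whether it already holds them.

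State in section 10.1 whether expected block weakness and postoperative pain count as adverse events or only as secondary outcomes.

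The cost is three rewritten lines, one added sentence and at most two tick-box fields, with no extra visits or staff.
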